## Glossary of terms

Assessment	A procedure used to generate data required by the study.
Biologic Samples	A biological specimen including, for example, blood (plasma, serum), saliva, tissue, urine, stool, etc. taken from a study participant.
Clinical Outcome Assessment (COA)	A measure that describes or reflects how a participant feels, functions, or survives.
Coded Data	Personal Data which has been de-identified by the investigative center team by replacing personal identifiers with a code.
Cohort	A group of individuals who share a common exposure, experience or characteristic, or a group of individuals followed up or traced over time.
Control drug	A study drug (active or placebo) used as a comparator to reduce assessment bias, preserve blinding of investigational drug, assess internal study validity, and/or evaluate comparative effects of the investigational drug.
Discontinuation from study	Point/time when the participant permanently stops receiving the study treatment and further protocol required assessments or follow-up, for any reason. No specific request is made to stop the use of their samples or data.
Discontinuation from study treatment	Point/time when the participant permanently stops receiving the study treatment for any reason (prior to the planned completion of study drug administration, if any). Participant agrees to the other protocol required assessments including follow-up. No specific request is made to stop the use of their samples or data.
Dosage	Dose of the study treatment given to the participant in a time unit (e.g. 100 mg once a day, 75 mg twice a day).
Electronic Data Capture (EDC)	Electronic data capture (EDC) is the electronic acquisition of clinical study data using data collection systems, such as Web-based applications, interactive voice response systems and clinical laboratory interfaces. EDC includes the use of Electronic Case Report Forms (eCRFs) which are used to capture data transcribed from source data/documents used at the point of care.
End of the clinical trial	The end of the clinical trial is defined as the last visit of the last participant or modify if different as defined by the protocol.
Enrollment	Point/time of participant entry into the study at which informed consent must be obtained. The action of enrolling one or more participants.

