## 2.1 Primary estimands

The estimand is the precise description of the treatment effect and reflects strategies to address events occurring during trial conduct which could impact the interpretation of the trial results (e.g. premature discontinuation of treatment).

For each subtype of CINDU, the primary clinical question of interest is: what is the treatment effect of the ligelizumab treatment versus placebo on the primary endpoint in participants with H1-AH as background medication, regardless of use of rescue medications and/or prohibited medications and treatment discontinuations due to either AE, or use of prohibited medications, or lack of efficacy, assuming that participants had never discontinued treatment due to other reasons or missed any treatment prior to Week 12 due to other non-human controlled emergency situations (e.g. COVID-19)?

The justification for the primary estimand is that it will capture both the effect of the study drug and the effect of additional background and rescue medications, mirroring the conditions in clinical practice. This will also enable an estimation of the effect of study drug for the full duration of the study. Further details can be found in [Section 5](#).

The primary estimand for each of the CINDU cohort is described by the following attributes:

- **Population:** participants receiving H1-antihistamines therapy at local-approved dose level as background medication suffering from symptomatic dermographism, cold urticaria, or cholinergic urticaria and meeting study inclusion/exclusion criteria (as listed in [Section 5.1](#) and [Section 5.2](#)). Further details about the population are provided in [Section 5](#).
- **Endpoint:**
  1. Symptomatic Dermographism: change from baseline to Week 12 in Total Fric Score (score derived based on results from the Fric Test 4.0, see [Section 8.3.1.1](#) for detail)
  2. Cold urticaria: change from baseline to Week 12 in critical temperature thresholds (CTT, i.e. the highest temperature hives are triggered, see [Section 8.3.1.2](#) for details) in response to the TempTest®
  3. Cholinergic urticaria: change from baseline to Week 12 in itch numerical rating scale (NRS) in response to the pulse-controlled ergometry (see [Section 8.3.1.3](#) for details).

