- **Treatment of interest:** ligelizumab or the placebo treatment (no further treatment for patients who discontinue treatment due to AE, lack of efficacy or intake of prohibited medications) with stable H1-antihistamines at local-approved doses as background medication + allowed rescue medication. The dose of the allowed background medication for CINDU must remain stable during the trial. Further details about the investigational treatment and control treatment are provided in [Section 6](#).
- **Handling of remaining intercurrent events:**
  1. Discontinuation of initial assigned study treatment prior to Week 12 due to adverse events (AE), use of prohibited medications or lack of efficacy (LoE): Participants who discontinue from study treatment early will be encouraged to stay in the study as detailed in [Section 9.1.1](#). Retrieved drop out (RDO) data collected after study treatment discontinuation will be used for analysis (treatment policy).
  2. Discontinuation of initial assigned study treatment prior to Week 12 due to reasons other than adverse events (AE), use of prohibited medications, or lack of efficacy

- (LoE): had participants taken the assigned treatment up to Week 12 (hypothetical strategy).
3. Use of prohibited medications prior to Week 12 and not result in treatment discontinuation: ignore (treatment policy).
  4. Missed treatment prior to Week 12 due to other non-human controlled emergency situations (e.g. COVID-19): had participants not missed treatment prior to Week 12 (hypothetical strategy).
- **The summary measure:**
    1. Symptomatic Dermographism: difference in mean change from baseline in Total Fric Score at Week 12 between treatments (ligelizumab 72 mg q4w vs placebo and ligelizumab 120 mg q4w vs placebo)
    2. Cold urticaria: difference in mean change from baseline of CTT at Week 12 between treatments (ligelizumab 72 mg q4w vs placebo and ligelizumab 120 mg q4w vs placebo)
    3. Cholinergic urticaria: difference in mean change from baseline in itch NRS in response to the pulse-controlled ergometry test at Week 12 between treatments (ligelizumab 120 mg q4w vs placebo)

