## 5.2 Exclusion criteria

Participants meeting **any** of the following criteria are **not** eligible for inclusion in this study.

1. Use of other investigational drugs within 5 half-lives of enrollment, or within 30 days for small molecules prior to the screening visit or until the expected pharmacodynamic effect has returned to baseline for biologics, whichever is longer.
2. History of hypersensitivity to any of the study drugs or its components or to drugs of similar classes (i.e. to murine, chimeric or human antibodies) or to the provocation test or items used in provocation tests
3. Participants who have concomitant CSU at screening
4. Participants who have a familial form (e.g familial cold autoinflammatory syndrome, familial cold urticaria) of the target CINDU that is being considered for the participant's inclusion in this study
5. Participants having a more defined other form of inducible urticaria than the target CINDU that is being considered for the participant's inclusion in this study
6. Diseases, other than chronic inducible urticaria, with urticarial or angioedema symptoms such as urticarial vasculitis, erythema multiforme, cutaneous mastocytosis (urticaria pigmentosa) and hereditary or acquired angioedema (eg, due to C1 inhibitor deficiency).
7. Any other skin disease associated with chronic itching that might influence, in the investigator's opinion, the study evaluations and results (eg, atopic dermatitis, bullous pemphigoid, dermatitis herpetiformis, senile pruritus, etc.) or skin diseases associated with only wheals and no itch e.g asymptomatic dermographism
8. Participants with evidence of helminthic parasitic infection as evidenced by stools being positive for a pathogenic organism according to local guidelines. All participants will be screened at Visit 1 (see Section 8.4). If stool testing is positive for pathogenic organisms, the participant will not be randomized and will not be allowed to rescreen.
9. Prior exposure to ligelizumab, omalizumab or other anti-IgE therapies.
10. Any H1-AH used as stable background medication at greater than local label approved doses after screening visit (Visit 1).
11. History or evidence of ongoing alcohol or drug abuse, within the last 6 months prior to randomization.
12. Inability to comply with study and follow-up procedures.
13. Use of prohibited treatment detailed in protocol ([Table 6-2](#)).

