### 6.2.2 Prohibited medication

Use of the class of treatments displayed in [Table 6-2](#) is NOT allowed after start of screening (Visit 1) and up until after the end of the follow-up period. The minimum required period without prohibited treatment before screening visit (Visit 1) is also listed in [Table 6-2](#). Each concomitant drug must be individually assessed against all exclusion criteria and the table below to see if it is allowed. If in doubt, the investigator should contact Novartis or delegate before randomizing a participant or allowing a new medication to be started.

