**Table 6-2 Prohibited medication**

Medication	Prohibition period prior to Screening visit (Visit 1)	Action taken if prohibited medication is administered
Omalizumab	No prior use allowed	Discontinue from study
Ligelizumab	No prior use allowed	Discontinue from study
Routine (daily or every other day during more than one consecutive day /month) doses of systemic corticosteroids*	30 days prior to Visit 1	Stop prohibited treatment

Medication	Prohibition period prior to Screening visit (Visit 1)	Action taken if prohibited medication is administered
IV/IM/IA corticosteroids	30 days prior to Visit 1	Stop prohibited treatment or discontinue from study treatment
Beta-blocker therapy	7 days prior to Visit 1	Stop prohibited treatment or discontinue from study treatment
Leukotriene antagonists	Stop at Visit 1	Stop prohibited treatment or discontinue from study treatment
H2-antihistamines	Stop at Visit 1	Stop prohibited treatment or discontinue from study treatment
First generation H1-antihistamines	Stop at Visit 1	Stop prohibited treatment or discontinue from study treatment
Hydroxychloroquine or chloroquine	30 days prior to Visit 1	Stop prohibited treatment or discontinue from study treatment
Other immunosuppressive and immunomodulatory medication with or without known effect on CINDU including but not limited to Methotrexate, cyclosporine A, cyclophosphamide, tacrolimus and mycophenolate mofetil, anti-IL-1, anti-TNF-alpha	30 days prior to Visit 1	Stop prohibited treatment or discontinue from study treatment
Intravenous immunoglobulin G	30 days prior to Visit 1	Discontinue study treatment
Plasmapheresis	30 days prior to Visit 1	Discontinue study treatment
Regular (daily or every other day) doxepin (oral)	14 days prior to Visit 1	Stop prohibited treatment or discontinue from study treatment
Vaccination with inactivated viruses	48 hours prior to each dosing visit (i.e. Week 0 to Week 20)	Stop prohibited treatment
Live attenuated vaccine	30 days prior to Visit 1	Discontinue study treatment

\*Corticosteroids (CS) with limited systemic exposure for non-CINDU indications can be used (e.g. Intra nasal or any topical CS) on an as-needed basis.

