If the prohibited treatment was used during the study for any indication, the participant must discontinue use of the prohibited treatment if the participant wishes to continue in the study. If the participant must continue a prohibited medication during the study, the participant must discontinue study treatment. If the participant receives a live virus vaccination during the study, the participant must discontinue study treatment.

Table 6-2 is not considered all inclusive. Medication should be assessed for adherence to the indication and other inclusion/exclusion criteria.

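### Table 6-2 takes randomized omalizumab (or non-study ligelizumab) users out of the study, while Sections 2.1 and 9.1.1 stop only study treatment for prohibited-medication users and seek visits to Week 12

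*Protocol*

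**What the plan says.** **Table 6-2 (Protocol Section 6.2.2).** The omalizumab and ligelizumab rows give the action "Discontinue from study". No other row does. The rest say to stop the prohibited drug, to stop study treatment, or offer either; IV immunoglobulin, plasmapheresis and live vaccine read *Discontinue study treatment*. The ban applies through screening, treatment and follow-up: use "is NOT allowed after start of screening (Visit 1) and up until after the end of the follow-up period".

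**Glossary.** Discontinuation from study is the point at which the participant "permanently stops receiving the study treatment and further protocol required assessments or follow-up, for any reason". Discontinuation from study treatment is a separate term, under which the participant agrees to the remaining assessments and follow-up.

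**Protocol Section 2.1 (repeated in SAP Section 1.2.1).** The clinical question asks for the effect "regardless of use of rescue medications and/or prohibited medications and treatment discontinuations due to either AE, or use of prohibited medications". Participants who stop treatment for prohibited medication are encouraged to stay, and their retrieved data are used under treatment policy. The treatment-of-interest attribute adds "no further treatment for patients who discontinue treatment due to AE, lack of efficacy or intake of prohibited medications".

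**Protocol Section 9.1.1.** Needing a prohibited treatment, or not complying with the prohibition, is a reason to stop study treatment. For anyone stopping treatment before Week 12, every effort is to be made to continue visits at least to Week 12.

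**Text below Table 6-2.** This is mixed. One sentence makes staying conditional: "the participant must discontinue use of the prohibited treatment if the participant wishes to continue in the study". The next requires a participant who must continue the drug to stop study treatment, and does not mention leaving the study.

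**SAP Section 2.5.3.** A provocation test at the end-of-treatment or end-of-study visit counts as Week 12 data only within 4 weeks either side of the planned Week 12 date. Otherwise the value is multiply imputed, using placebo information in the ligelizumab arms and under MAR in the placebo arm.

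**The concern.** A site that follows the table removes a participant whom Sections 2.1 and 9.1.1 ask it to keep. Leaving the study is the natural action during screening, where "Prior exposure to ligelizumab, omalizumab or other anti-IgE therapies" is an exclusion. The conflict arises only for randomized participants. For them the issue is in practice the omalizumab row, because ligelizumab is the study drug and the ligelizumab row can only mean non-study supply.

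Two things are at stake:

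- **Efficacy data.** A Week 12 value that could have been observed becomes an imputed one, for an event where the estimand section plans to use what is observed.
- **Safety data.** Scheduled follow-up visits end in someone who has received study drug or placebo and then a further anti-IgE antibody, although treatment-emergent events are counted to 16 weeks after the last dose (Protocol Section 12.5.2).

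**Working it through.** The plan gives no figure for this event. The planning inputs used below do reproduce the stated powers by a two-sample t-test after 10% drop-out: 93.7% for dermographism (50 per arm, difference 1.3, SD 1.7, one-sided 1.25%), and 99.4% against the stated >99% for cold urticaria (30 per arm, difference 10, SD 8, one-sided 1.25%).

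**1. Which exits lose the Week 12 value.** Study day = 1 + 7 × week, so Week 12 is Day 85 and the window is 85 ± 28, or Days 57 to 113. A test on Day 29 (Week 4) is outside; Day 57 (Week 8) is the first scheduled test inside. Protocol Section 8 holds the final visit as soon as possible after exit, so an exit before about Day 57 usually leaves no usable result. "Usually" is needed because a delayed final visit could fall inside the window.

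**2. Which endpoints are affected.** The primary endpoints and the continuous itch NRS secondary endpoints. Under SAP Section 2.6.3, responder endpoints score participants who stop treatment for prohibited medication as non-responders, so observed or imputed values do not matter there.

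**3. Size, if the question is the effect regardless of prohibited medication.** The imputed value contains no omalizumab benefit, so

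shift = (uptake in placebo − uptake in ligelizumab) × omalizumab effect,

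where a positive shift favours ligelizumab. The effects come from the omalizumab trials cited in Protocol Section 12.8.1:

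| | Total Fric Score (56 per arm) | CTT (34 per arm) |
|---|---|---|
| Effect, 150 mg | 1.78 − 0.6 = 1.18 | 10.6 − 0.3 = 10.3 °C |
| Effect, 300 mg | 2.0 − 0.6 = 1.40 | 10.4 − 0.3 = 10.1 °C |
| Per net placebo-arm user | 1.18/56 = 0.021 to 1.40/56 = 0.025 | 10.1/34 = 0.297 to 10.3/34 = 0.303 °C |
| Share of planned difference | 1.6–1.9% of 1.3 | 3.0% of 10 °C |
| Standard error of the difference | 1.7 × √(2/50) = 0.34 | 8 × √(2/30) = 2.07 °C |
| Net users for a 10% shift | 0.13/0.025 = 5.2 to 0.13/0.021 = 6.2, so 6–7 people | 1.0/0.303 = 3.3 to 1.0/0.297 = 3.4, so 4 people |

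The documents give no rate of anti-IgE use. At an assumed 0–3% per arm, the extremes are 0.03 × 1.40 = 0.042 points and 0.03 × 10.3 = 0.31 °C in either direction, at most 3.2% of the planned difference. At equal uptake the shift is 0. These are upper bounds: every user is given the full cited effect and no usable Week 12 value.

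**4. Size, if the treatment of interest is read as no further treatment.** A value without omalizumab benefit is then arguably the target, and the bias is 0.

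**5. Cholinergic cohort.** The cited omalizumab trial is summarised only by overall medians and response rates, so no shift is computed.

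**6. Safety.** The window for treatment-emergent events is 16 weeks (112 days) after the last dose. After study exit there remain the final visit, AE monitoring for at least 30 days after the last dose, and SAE reporting to 30 days after the last visit. Suspected-related SAEs stay reportable later, and detected AEs are followed to resolution or until judged permanent (Protocol Sections 10.1.1 and 10.1.3). What is lost is the scheduled follow-up visits.

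**The case against.** The best defence is that a specific row overrides a general rule. Section 9.1.1 refers to Section 6.2.2, which contains the table; Section 6.2.1 lets the sponsor decide whether an enrolled participant should continue; and the study population rationale singles out prior anti-IgE exposure as a possible influence on outcome. This makes the table intelligible, and it may justify stopping study treatment, which is not questioned here. It gives no reason to end observation under a treatment-policy strategy, and no section says that anti-IgE drugs are handled differently after randomization.

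Three further points stand in part:

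- **The missing value is already provided for.** It is: imputation is pre-specified. Section 9.1.1 also accepts telephone contact for a minimum data set, so changing the cells does not guarantee a Week 12 test. It does remove the instruction that prevents one.
- **The fix could add an off-target value.** Under the no-further-treatment wording, an omalizumab-affected result would be off target. A value that has been collected can be set aside; one never collected cannot be recovered.
- **The trial stopped.** The SAP records 39 participants enrolled and 3 with a completed Week 12 visit, and runs no efficacy analysis. No reported result is affected.

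A reader might infer that the row biases the trial in favour of ligelizumab. The documents do not support this. Under one reading a placebo-arm user favours ligelizumab and a ligelizumab-arm user counts against it; the net depends on unknown uptake, and the other reading gives zero.

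A reader might also subtract 30 from 112 and report 82 days without safety visits. The 30 days are a minimum AE-monitoring period and not a visit schedule, so the difference does not measure a visit gap.

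**Conclusion.** The inconsistency is real, but its consequence is minor. Followed as written, the omalizumab row (and the ligelizumab row for non-study supply) turns an obtainable Week 12 value into an imputed one for a randomized user who exits before about Day 57. It also ends scheduled safety follow-up for any such user. The shift per net placebo-arm user is about 0.06–0.07 standard errors for Total Fric Score and 0.14–0.15 for CTT, before allowing for equal uptake or the alternative estimand reading, either of which brings it to zero. The sizes rest on the cited omalizumab effects carrying over in full, and the 3.2% ceiling rests on an assumed uptake of 0–3%. The conflict itself rests only on the text. This is a cheap improvement to the plan as designed and not a threat to its conclusions.

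**What to change.** For randomized participants, change the omalizumab and ligelizumab cells to *Discontinue study treatment*, with provocation tests sought as scheduled to Week 12 and the scheduled safety follow-up visits kept. Use during screening stays a screen failure.

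The cost is two table cells and about seven extra visits at most per user: Weeks 4, 8 and 12, the end-of-treatment visit and three follow-up visits. An exit before Day 8 could add the Week 1 visit, while the end-of-treatment visit coincides with a scheduled one when dosing is on time. At the assumed 0–3% uptake this concerns 0 to 1.7 people per 56-person arm (0.03 × 56) and 0 to 1.0 per 34-person arm (0.03 × 34).

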### 6.2.3 Rescue medication

If unbearable symptoms occur during the study, investigators must instruct participants on the acceptable treatment for managing their disease with the use of rescue medication, thereby allowing participants to continue in the study as long as possible. Investigators must instruct participants to assess the need for rescue medication on a day-by-day basis, following the limitations for H1-AH rescue medications and adhering to local regulations. It is only during the 24 hours prior to the provocation visit, participants must avoid taking any rescue medication (see Section 3.2).

In addition to being used as background medication (see [Section 6.2.1](#)), non-sedating H1-AH fexofenadine, loratadine, desloratadine, cetirizine, levocetirizine and rupatadine, will also be allowed as rescue medication used on an as needed basis for participants with flare-ups of unbearable symptoms of their disease during screening, treatment and follow-up periods. The selection of a H1-AH rescue medication should be made only once for an individual participant. For each individual participant, the H1-AH rescue medication used must differ from the H1-AH used for background medication (see [Section 6.2.1](#)), in order to avoid the potential use of H1-AHs at non-approved doses. A switch of the H1-AH rescue medication for an individual participant is not permitted except due to an AE or if the medication is no longer available in the country.

Rescue medication will be sourced locally. [REDACTED]

[REDACTED] Participants will be asked to return all unused rescue medication at the end of the study or at the time of discontinuation from the study.

